- Local laboratory results may be used for dosing decisions; however, all samples (other than thyroid function tests) must still be sent to the central laboratory until the occurrence of progression, death, the start of subsequent systemic antineoplastic therapy, study termination, or until 6 months after the discontinuation of study treatment, whichever occurs first. Chemistry will consist of albumin, ALT, alkaline phosphatase, AST, HCO3- or CO2, blood urea nitrogen, calcium, chloride, magnesium, potassium, sodium, phosphate, creatinine, total bilirubin, LDH, urate, blood glucose (nonfasting), and standard C-reactive protein and may be collected up to 3 days prior to dosing. Thyroid function tests (thyroid stimulating hormone, free or total T3, and free or total T4) will be performed during screening, Cycle 3, and every 3 cycles thereafter and will be analyzed locally. Serum β2 microglobulin levels will be measured at screening only and must be done by central laboratory (see Section 9.3.9.6 for further details on chemistry evaluations) It is not necessary to repeat these tests on C1D1 predose if the tests performed at screening are less than 3 days old.
- As required by country regulations, hepatitis B serology (HBsAg, hepatitis B core antibody, hepatitis B surface antibody) and hepatitis C serology will be performed at screening. Patients with known chronic hepatitis C and/or positive serology (unless due to vaccination or passive immunization due to Ig therapy) for chronic hepatitis B are excluded. Patients who are seropositive for hepatitis B (defined as a positive test for HBsAg) are excluded. Patients with

resolved infection (that is, participants who are HBsAg negative but positive for antibodies to hepatitis B core antigen and/or anti-HBs) must be screened using real-time PCR measurement of HBV DNA levels. Those who are PCR positive will be excluded. *Exception*: Patients with serologic findings suggestive of HBV vaccination (anti-HBs positivity as the only serologic marker) and a known history of prior HBV vaccination do not need to be tested for HBV DNA by PCR.

- Urinalysis (dipstick) includes bilirubin, glucose, ketones, leukocytes, nitrite, occult blood, pH, protein, specific gravity, turbidity and color, and urobilinogen. Microscopic analysis only if clinically indicated: bacteria, RBCs, WBCs, casts, and crystals.
- 1. Pregnancy test (refer to Section 9.3.9.2).

Screening/baseline: Participants of childbearing potential must have 2 negative pregnancy tests before starting study drug.

- A urine or serum pregnancy test will be required during screening (within 10 to 14 days before start of study drug); this test must be negative.
- A urine or serum pregnancy test must be performed at baseline (within 24 hours before the start of study drug). The results from these tests must be available and negative before the first dose of study drug is administered.

On-treatment: During the study, participants of childbearing potential must have a negative urine or serum pregnancy test result within 72 hours before dosing on Day 1 of each cycle during treatment prior to dosing.

- If a menstrual period is delayed, absence of pregnancy in participants of childbearing potential must be confirmed by a negative urine or serum pregnancy test.
- Pregnancy tests may also be repeated during the study as per request of IRB or if required by local regulations.

EOT: At EOT, a urine or serum pregnancy test is required in participants of childbearing potential.

- m. All responses, including PD, must be confirmed by central laboratory evaluation. If the start of a cycle is delayed, serum M-protein and serum FLCs are to be collected for central laboratory analysis if not previously sent within the preceding 10 days. If a patient has collected a 24-hour urine sample and brought it to a visit, the sample should be sent for central laboratory analysis of urine M-protein even if not on Day 1 of a cycle.
- n. Screening levels for Part 3 must be ≥500 mg/dL. To be repeated at baseline (C1D1) if screening sample was taken more than 7 days before C1D1.
- o. Sample to be collected at any time on Day 2 of the cycle.
- ^{p.} Urine M-protein 24-hour urine sample required while on treatment and during follow-up. To be repeated at baseline (C1D1) if screening sample was taken more than 7 days before C1D1.
- 9. Serum FLC to be repeated at baseline (C1D1) if screening sample was taken more than 7 days before C1D1.
- Immunofixation in serum and urine is required for patients evaluated for CR; see Sections 9.3.10.6. To be repeated at baseline (C1D1) if screening sample was taken more than 7 days before C1D1.
- A blood sample for quantification of Ig (IgM, IgG, and IgA) will be obtained. For the rare patient with known IgD or IgE MM, the quantitative test for that antibody will be followed at the same time points throughout the treatment period and PFS follow-up period as quantitative IgS (in addition to quantitative IgM, IgG, and IgA) (see Section 9.3.10.3). To be repeated at baseline (C1D1) if screening sample was taken more than 7 days before C1D1.
- For local analysis of disease assessment and cytogenetics at screening, a standard BMA drawn before consent is acceptable provided this is collected within 5 weeks of the first dose. All patients should also have a sample from screening sent for central cytogenetic analysis ("BMA for cytogenetics").
- u. Blood samples for PK will be collected at time points specified in Appendix C, Tables 9 and 10.
- v. All patients should have a fresh BMA sample from screening sent for central cytogenetic analysis.
- w. Predose.
- x. Coagulation panel (prothrombin time/international normalized ratio, activated partial thromboplastin time, fibrinogen, D-Dimer) to be performed if clinically

significant bleeding occurs.

- Blood samples for immunogenicity (ADA/NAb) testing will be collected before the dose on indicated visits during treatment and, if possible, at the EOT visit. In case of an infusion reaction, blood draws should be performed for central evaluation of immunogenicity (see Section 8.7.1.1). On days when dosing is not required, samples may be collected at any point during the clinic visit.
- ^{z.} Only repeat tests in parentheses for patients terminating treatment due to PD if they were not performed before for PD determination at the last visit, and for patients in CR if not performed before for CR confirmation.
- End-of-treatment laboratory assessments are to be performed prior to the patient starting a new treatment or a maximum of 30 days following the last dose.
- Patients will have PFS follow-up every 4 weeks from the EOT visit until the occurrence of PD, death, the start of subsequent systemic antineoplastic therapy, study termination, or until 6 months after the discontinuation of study treatment, whichever occurs first.
- cc. OS follow-up continues every 12 weeks until death, study termination, or patient withdrawal.
- dd. Predose and at 4 hours (\pm 60 minutes) after the end of infusion.
- All PROs should be administered D8 of each cycle, except for C1 when the EORTC QLQ-MY20 should be administered on D1 and D8 (ie, C1D1 and C1D8) and the EQ-5D-5L on D1 (ie, C1D1). On C1D1, PROs may be completed within a +1-day window, and on the rest of the days PROs may be completed within a 2-day window. On days when PROs are administered during clinic visits, the EORTC QLQ-MY20 and EQ-5D-5L should be administered to patients when they arrive for their scheduled visits, before any clinical measurements, assessments, evaluations, or procedures being performed (see Section 9.3.12). On days when PROs are not completed at the clinic (ie, Day 8 of each cycle starting with Cycle 3), site staff should remind each patient at every cycle to complete their PROs. Healthcare utilization data is collected on D1 of every cycle, starting at C1, and at EOT.
- Immediately following the bone marrow aspiration/biopsy obtained for local disease assessment at screening and for confirmation of a suspected CR, BMA will be collected for evaluation of minimal residual disease and sent to a central laboratory for analysis. If a BMA/biopsy drawn before consent, within 5 weeks of first dose, is used for local disease assessment at screening, the first BMA pull will be drawn for the MRD sample. Additionally, BMAs will be requested for MRD assessment every 6 months after suspected CR to further characterize MRD status. Screening MRD samples will be obtained in China based on acceptability of method chosen.
- Following the collection of BMA for MRD sample at screening, an additional 3 mL pull of BMA will be collected for cytogenetic analysis and central evaluation of both tumor and immune fractions of bone marrow.
- hh. Sample collection not applicable to patients enrolled in China. See Sections 9.3.11.3.2.6, 9.3.11.3.2.7 and 9.3.11.4.
- Cytogenetic results from samples taken within 5 weeks prior to first dose are acceptable for stratification. If a previous result is not available and the patient is known to have high-risk disease [ie, del17, t(4;14) and/or t(14;16)] from prior cytogenetic testing, regardless of timing, they should be stratified as high risk for the purpose of enrollment. Additionally, all patients should have a sample from screening sent for central cytogenetic analysis ("BMA for cytogenetics").
- ji. A portion of this sample will be used for exploratory analyses.
- kk. See Section 9.3.10.7 for details regarding interference testing for patients who received an IgG MAb as recent prior therapy.
- ^{II.} For patients who have had a response to modakafusp alfa treatment, a 3mL BMA collection at progression is optional. Sample to be used for central evaluation of both tumor and immune fractions of the bone marrow to inform potential resistance mechanisms.

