- 8. Patient has a history of acute myocardial infarction within 5 months from enrollment or has electrocardiogram (ECG) abnormalities during screening that are deemed medically relevant by the investigator.
- 9. Patient has QT interval corrected by the Fridericia method (QTcF) >480 msec (Grade ≥2).
- 10. Patient has a concurrent illness that would preclude study conduct and assessment including, but not limited to, uncontrolled medical conditions, uncontrolled and active infection (considered opportunistic, life-threatening, or clinically significant), uncontrolled risk of bleeding, uncontrolled diabetes mellitus, pulmonary disease (including obstructive pulmonary disease, pulmonary fibrosis, and history of symptomatic bronchospasm), alcoholic liver disease, or primary biliary cirrhosis.
- 11. Patient has a chronic condition requiring the use of systemic corticosteroids >10 mg/day of prednisone or equivalent.
- 12. Patient has clinical signs of central nervous system involvement of MM.
- 13. Female patients who are lactating and breastfeeding or have a positive urine or serum pregnancy test during the screening period or a positive urine or serum pregnancy test on Day 1 before first dose of study drug if applicable.
- 14. Any serious medical or psychiatric illness that could, in the investigator's opinion, potentially interfere with the completion of treatment according to this protocol.
- 15. Patient has a known history of human immunodeficiency virus.
- 16. Parts 1 and 2: Known chronic hepatitis C and/or positive serology (unless due to vaccination or passive immunization due to Ig therapy) for chronic hepatitis B.
 - Japan Safety Lead-In and Part 3: Known chronic hepatitis C and/or positive serology for chronic hepatitis B (unless due to vaccination or passive immunization due to Ig therapy), or hepatitis B virus (HBV) or hepatitis C virus (HCV) infection. Seropositive for hepatitis B (defined by a positive test for hepatitis B surface antigen [HBsAg]). Participants with

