resolved infection (that is, participants who are HBsAg negative but positive for antibodies to hepatitis B core antigen and/or antibodies to hepatitis B surface antigen [anti-HBs]) must be screened using real-time polymerase chain reaction (PCR) measurement of HBV DNA levels. Those who are PCR positive will be excluded. Seropositive for hepatitis C (anti-HCV antibody positive or HCV-RNA quantitation positive). *EXCEPTIONS*: Participants with serologic findings suggestive of HBV vaccination (anti-HBs positivity as the only serologic marker) AND a known history of prior HBV vaccination do not need to be tested for HBV DNA by PCR; participants with hepatitis C who are seropositive but with a sustained virologic response (defined as absence of viremia at least 12 weeks after completion of antiviral therapy).

- 17. Patient has a history of severe allergic or anaphylactic reactions to recombinant proteins or excipients used in modakafusp alfa formulation.
- 18. The patient is currently participating in another antimyeloma therapeutic clinical study.
- 19. Previous treatment with modakafusp alfa.

Part 3: In addition to the above criteria, patients must not have plasma cell leukemia or have had primary refractory MM, current central nervous system involvement of MM, myelodysplastic syndrome, myeloproliferative syndrome, or have had a second malignancy within the previous 3 years, except treated basal cell or localized squamous skin carcinomas, localized prostate cancer, cervical carcinoma in situ, resected colorectal adenomatous polyps, breast cancer in situ, or other malignancy for which the patient is not on active anticancer therapy.

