or total T3, and free or total T4) will also be performed. Serum β2 microglobulin levels will be measured at baseline only. It is not necessary to repeat these tests on C1D1 predose if the tests performed at screening are less than 4 days old. Hepatitis B serology (hepatitis B surface antigen, hepatitis B core antibody, hepatitis B surface antibody) and hepatitis C serology will be performed at screening. Patients with known chronic hepatitis C and/or positive serology (unless due to vaccination or passive immunization due to Ig therapy) for chronic hepatitis B are excluded.

- h. Hematology will consist of hemoglobin, hematocrit, platelet count, WBC count, and WBC differential (basophils, eosinophils, lymphocytes, monocytes, neutrophils). It is not necessary to repeat these tests on C1D1 predose if the tests performed at screening are less than 4 days old.
- ^{i.} Urinalysis (dipstick) will include bilirubin, glucose, ketones, leukocytes, nitrite, occult blood, pH, protein, specific gravity, turbidity and color, and urobilinogen. Microscopic if clinically indicated only: bacteria, RBCs, WBCs, casts, and crystals.
- Pregnancy test (refer to Section 9.3.9.2).
 - Screening/Baseline: Participants of childbearing potential must have 2 negative pregnancy tests before starting study drug.
 - o A urine or serum pregnancy test will be required during screening (within 10 to 14 days before start of study drug); this test must be negative.
 - O A urine or serum pregnancy test must be performed at baseline (within 24 hours before the start of study drug). The results from these tests must be available and negative before the first dose of study drug is administered.
 - On-treatment: During the study, participants of childbearing potential must have a negative urine or serum pregnancy test result within 72 hours before dosing on Day 1 of each cycle during treatment prior to dosing. If a menstrual period is delayed, absence of pregnancy in participants of childbearing potential must be confirmed by a negative urine or serum pregnancy test.
 - o Pregnancy tests may also be repeated during the study as per request of IRB or if required by local regulations.
 - EOT: A urine or serum pregnancy test is required at EOT in participants of childbearing potential.
- k. To be repeated at baseline (C1D1) if screening sample was taken more than 7 days before C1D1.

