- s. Antiplatelet antibodies will be collected and analyzed locally until the sponsor communicates to the sites that a sufficient number of samples have been obtained to stop the collection.
- ^t Coagulation panel (prothrombin time/international normalized ratio, activated partial thromboplastin time, fibrinogen, D-Dimer) to be performed if clinically significant bleeding occurs.

Appendix A Table 12 Part 3 Extension Schedule of Events: Screening, Baseline, Cycle 1, and Cycle 2											
Study Period	Screening	Treatment Phase – Cycle 1					Treatment Phase – Cycle 2				
Cycle Day		C1D1	C1D2	C1D8	C1D15	C1D22	C2D1	C2D2	C2D8	C2D15	C2D22
Window Allowed	≤21	0	0	±2 d	±2 d	±2 d	±2 d	±0 d	±2 d	±2 d	±2 d
Informed consent ^a	X										
Eligibility criteria	X										
Demographics	X										
Medical history	X										
Prior medication and treatment history	X										
Height and weight ^b	X						X				
ECOG performance status	X						X				
12-lead ECG °	X	X		X	X		X				
Physical examination (may be symptom-directed following screening visit)	Х	X		х			X				
Vital signs ^d	X	X		X	X	X	X		X	X	X
Monitoring of concomitant medication and procedures	Recorded from signing of the ICF through 30 days after last dose of study drug or start of subsequent anticancer therapy, whichever occurs first.										
AE reporting	Recorded from signing of the ICF through 30 days after last dose of study drug or start of subsequent anticancer therapy, whichever occurs first.										
	SAEs will be reported from signing of ICF through 30 days after last dose of study drug, even if the patient starts nonprotocol therapy.										
Dosing											
Modakafusp alfa infusion ^f		X					X				
Safety Laboratory Assessments											
Chemistry i (central analysis)	X	(X)		X	X	X	X		X	X	X
Hematology ^g (central analysis)	X	(X)		X	X	X	X		X	X	X
Thyroid function tests i (local analysis)	X										
Urinalysis k(local analysis)	X						X				
Pregnancy test ¹ (local analysis)	X	X					X				

Study Period	Screening		Traatma	nt Phas	e – Cycle	1		Treatmen	t Phase _	Cycle 2	
Cycle Day	Streening	C1D1			C1D15		C2D1	C2D2	C2D8	C2D15	C2D22
Window Allowed	<21	0	0	±2 d	±2 d	±2 d	±2 d	±0 d	±2 d	±2 d	±2 d
Serology ^j (local analysis)	(X)										
Coagulation panel * (local analysis)			To be	ındertak	en if clin	ically sign	ificant ble	eding is ob	served.	 	1
Disease Assessments											
Serum M-protein m, n (central analysis)	X	(X) n		Π			X		I	Ι	

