Germany	7.1 Inclusion Criteria #8	7 days	Agree to practice 1 highly effective method of contraception and 1 additional effective (barrier) method at the same time, from the time of signing the informed consent through 6 months 7 days after the last dose of study drug, OR - Agree to practice true abstinence, when this is in line with the preferred and usual lifestyle of the subject, from the time of signing the informed consent through 6 months 7 days after the last dose of study drug. (Periodic abstinence [eg, calendar, ovulation, symptothermal, postovulation methods], withdrawal, spermicides only, and lactational amenorrhea are not acceptable methods of contraception. Female and male condoms should not be used together.) - Agree not to donate an egg or eggs (ova) during the study and for 6 months 7 days after the last dose of study drug.
Germany	Inclusion Criteria #9	unless for over a year 7	Male patients, even ifunless surgically sterilized (ie, status postvasectomy) for over a year, who: • Agree to practice effective barrier contraception during the entire study treatment period and through 1207 days after the last dose of study drug, OR • Agree to practice true abstinence, when this is in line with the preferred and usual lifestyle of

	Summary of Changes				
Country	Section Number	Country Specific Language	Country Specific Language in Tracked Changes against Global Protocol Language		
			the subject. (Periodic abstinence [eg, calendar, ovulation, symptothermal, postovulation methods], withdrawal, spermicides only, and lactational amenorrhea are not acceptable methods of contraception. Female and male condoms should not be used together.) • Agree not to donate sperm during the study and for 1207 days after the last dose of study drug.		
Germany	7.2 Exclusion Criteria	14. Infection with HIV: Screening for HIV infection will be performed, and patients who have a positive result will be excluded.	14. Infection with HIV: Screening for HIV infection will be performed, and patients who have a positive result will be excluded.		
Germany	7.2 Exclusion Criteria	15. Screening for HBV and HCV infection will be performed.	Part 3: Hepatitis B virus (HBV) or hepatitis C virus (HCV) infection. Screening for HBV and HCV infection will be performed.		

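### Part 3 exclusion 16 depends on hepatitis B and C test results, but the Part 3 schedule orders those tests only where country rules require them

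*Protocol*

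**What the plan says.** Criterion 16 in Protocol Section 7.2 has a separate text for the Japan safety lead-in and Part 3. Part of it works from history (known chronic hepatitis C), but most of it works from test results:

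- Hepatitis B surface antigen: "Seropositive for hepatitis B (defined by a positive test for hepatitis B surface antigen [HBsAg"]).
- Resolved hepatitis B: patients without surface antigen but with core and/or surface antibody "must be screened using real-time polymerase chain reaction (PCR) measurement of HBV DNA levels", and "Those who are PCR positive will be excluded". Patients whose only marker is surface antibody and who have a known vaccination history are spared the PCR.
- Hepatitis C: "Seropositive for hepatitis C (anti-HCV antibody positive or HCV-RNA quantitation positive"), with an exception for seropositive patients who have a sustained virologic response.

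The Part 3 schedule of events (Appendix A Table 12) has a row "Serology ^j (local analysis") with `(X)` in the screening column. The general note under the Part 3 tables says that a cross in parentheses is a test done only in the circumstances given in its footnote. Footnote j gives the circumstance: "As required by country regulations, hepatitis B serology".

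The corresponding footnote for Parts 1 and 2 (footnote g) has no such condition: hepatitis B markers "and hepatitis C serology will be performed at screening".

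**The concern.** An exclusion defined by a test result can be applied only if the test is done. In Part 3 the criterion is more detailed than in Parts 1 and 2, yet the instruction to test is weaker. A site in a country with no regulation on the matter could do exactly what the schedule asks and have no HBsAg or anti-HCV result. The PCR step would then never be triggered, because it starts from an antibody result.

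Two things are at stake. The first is patient safety at entry: the criterion is meant to keep these patients out. The second is consistency: whether the test-based exclusions operate would depend on the country and not on the protocol. Baseline hepatitis status also helps in reading later events. Section 4.5.1 lists raised liver enzymes among possible adverse drug reactions, and Section 10.2 leaves causality to the investigator's yes-or-no judgment.

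**Working it through.** No arithmetic applies. The check sets the passages side by side.

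1. **What criterion 16 needs in Part 3.**

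| Part of the criterion | Information needed |
|---|---|
| Known chronic hepatitis C | History |
| HBsAg positive | HBsAg test |
| Resolved hepatitis B, then HBV DNA | Core and surface antibody, then PCR |
| Anti-HCV or HCV RNA positive | Hepatitis C test |

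2. **What the Part 3 schedule supplies.** Table 12 shows serology at screening as `(X)`, and footnote j ties it to country regulations. In Table 13 (Cycle 3 onward) the serology row is empty. Screening is therefore the only scheduled opportunity, and it is conditional.

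3. **Whether other global Part 3 text fills the gap.** Section 9.3.9.6 and its Table 9.a list the chemistry and hematology tests and contain no hepatitis markers. Criterion 16 itself orders only the PCR, and only for patients whose antibodies have already been found. No other global Part 3 passage orders the serology for all patients.

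4. **Comparators inside the protocol.** In Parts 1 and 2, footnote g orders hepatitis B and C serology without condition. In Appendix J, the German local text says "Screening for HBV and HCV infection will be performed", and the Czech local text carries the same sentence. Those two countries are covered.

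5. **Following one patient through.** Take an undiagnosed carrier at a site with no country rule and no local text. History shows nothing. The schedule orders no serology. No HBsAg or anti-HCV result exists, and no antibody result exists to trigger the PCR. None of the test-based parts of criterion 16 can be shown to be met, and the patient could be enrolled.

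6. **Footnote j against criterion 16 on content.** Footnote j repeats the hepatitis B parts: surface antigen, PCR for resolved infection, and the vaccination exception. On hepatitis C it mentions only known chronic disease. The exclusion for anti-HCV or HCV RNA positivity is absent, and so is the sustained-response exception that belongs to it. Footnote j is an incomplete copy of the criterion.

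**The case against.** The strongest defence is that the body of the protocol already binds the site. Section 6.4 places randomization after eligibility has been fully assessed, Section 8.1 requires the criteria for giving study drug to be met and documented, and Section 14.2 allows no exemptions from the eligibility criteria. On that reading, a site with no serology cannot document criterion 16, whatever footnote j says. This stands as an argument that the passages are in tension. It does not remove the gap: the site then has one text that implies a test and another that makes the test conditional, and the schedule is where the test would be ordered.

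Some mitigation is also real. The history-based part catches known hepatitis C. Inclusion criterion 6 limits ALT/AST and bilirubin, and chemistry is repeated on treatment. These are not hepatitis tests, and criterion 16 does not accept them as substitutes.

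Four stronger readings are tempting and are not supported:

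- *The two texts contradict each other on the patient with a sustained virologic response.* Both exclude known chronic hepatitis C in like terms. The exception in criterion 16 follows the seropositivity exclusion, which footnote j does not contain. The defect is an omission and not a shown contradiction.
- *Germany had to repair the current footnote.* The German text belongs to a local version of Amendment 8 (August 2022) and was tracked against that wording. Amendment 9 (August 2023) later revised the hepatitis text. The German and Czech sentences show that those countries are covered, not why.
- *A headcount of missed carriers.* The documents give no prevalence, do not say which countries lack a testing rule, and do not say whether any Part 3 site is in one. Applying an assumed prevalence to all 236 patients would count patients who are tested anyway.
- *Missed carriers would trip the Part 3 safety boundaries.* A single case cannot reach 4 of 10, 11 of 35 or 20 of 65 Grade 4 or higher events. The death boundary of 1 in 10 would need a carrier, a flare, a fatal outcome and attribution to the drug, and crossing it pauses enrollment until the IDMC reviews the data. The documents do not describe hepatitis reactivation as a risk of this drug.

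**Conclusion.** The inconsistency is real: Part 3 criterion 16 presupposes serology that the Part 3 schedule makes conditional on country regulations. It rests on the text alone and needs no assumption about prevalence. The practical effect is that, outside Germany and the Czech Republic and wherever no country rule requires testing, a site may lack the results needed to apply the test-based exclusions. How many patients or sites that covers cannot be derived from the documents, and it could be none. The point concerns eligibility and patient safety at entry; the Part 3 sample size, power and ORR analysis are not affected. It should be corrected because the plan's own criterion cannot otherwise be applied uniformly and the remedy is small.

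**What to change.** Reconcile Table 12 and footnote j with criterion 16 so that the schedule supplies, before randomization, the results the criterion needs for every Part 3 patient. One way is to make the screening serology cell unconditional and remove the country condition from footnote j, as Parts 1 and 2 already do. Have footnote j refer to criterion 16 instead of restating part of it, so that the hepatitis C exclusion and its exception stand in one place only.

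The cost is a table-cell and footnote edit, plus one local blood test per patient at sites not already testing, with PCR where criterion 16 already calls for it. Footnote a to the Part 3 tables already accepts routine-care results obtained within the screening window, so some patients would need no extra sample. The change matters only for patients still to be enrolled, including any in the China continuation cohort.
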